### **8.2.1 Primary Efficacy Analysis**

A likelihood-based Mixed Model Repeated Measures (MMRM) will be used to assess the primary objective. MMRM is the best method to control type I error rate and minimize bias in the presence of missing data. In the model, the SKAMP total score for each timepoint will be analyzed with the fixed effects of sequence (two levels), period (two levels), treatment (two levels) and time (10 levels, one for each of 30 minutes prior and 1, 2, 3, 4.5, 6, 7, 9, 10, and 12 hours post dosing) while the repeated measures effect of timepoint will be defined for subject and “Variance Components (VC)” covariance structure.

The two treatment levels will be: d-ATS (5, 10, 15, 20 mg doses combined) and placebo. The sequence effect (treatment x period interaction) will be tested at the significance level of 0.10. If significant differences are detected between sequences, data will be reviewed and strength of evidence indicating a crossover effect will be considered. In this case data from Visit 6 only will be presented to aid in assessment of the treatment effect. When only one period of data is used then the efficiencies gained from conducting a crossover trial design may be lost and there is concern associated with treating data as a parallel study due to the sample size being based up on the assumed efficiencies and may no longer be large enough to provide sufficient power. In this case, permutation test will be used to validate the results. Sampling without replacement (i.e. duplicate samples are not allowed) will be performed for 5000 permutations. The average mean treatment difference will be presented along with the associated 95% confidence interval and p-value for the permutation test. This will be compared against a significance level of 0.05. The primary efficacy analysis on the FAS population will also be conducted for the following subgroups:

- Investigator Site
- Optimized dose
- Gender
- ADHD type (inattentive, hyperactive/impulsive, combined, not otherwise specified)
- Baseline ADHD severity (defined as the pre-dose ADHD rating scale at baseline, Visit 0).
- Age group

Amendment 4: Version 5.0 May-08-2013

Amendment 3: Version 4.0 December-11-2012

Amendment 2: Version 3.0 October-31-2012

Amendment 1: Version 2.0 August-02-2012

Final Protocol May-25-2012

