1. INTRODUCTION

This statistical analysis plan (SAP) describes the statistical methods to be used during the reporting and analyses of data collected under Noven Pharmaceuticals, Inc. Protocol: N25-006.

The format and content of this SAP are structured to provide sufficient detail to meet the requirements specified by the International Conference on Harmonization (ICH) E9: Guidance on Statistical Principles in Clinical Trials.

This SAP should be read in conjunction with the study protocol and case report form (CRF). This version of the plan has been developed using the protocol amendment 4 dated 08MAY2013 and version 2.0 of the CRF dated 05MAR2013. Any further changes to the protocol or CRF may necessitate updates to the SAP.

The SAP is to be developed in two stages. The purpose is to “finalize” a SAP so that programming can be started early in the process. Versions of the SAP up to initial sponsor approval will be known as SAP1. Changes following approval of SAP1 will be tracked in the SAP Change Log and a final version of the SAP, known as SAP2, will be issued for sponsor approval prior to database lock.

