6. ANALYSIS POPULATIONS

6.1 FULL ANALYSIS SET

The full analysis set (FAS) includes all consented and randomized subjects who have taken at least one dose of study medication. The FAS population will be used as the primary population for analysis of efficacy endpoints.

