7.1.1 Primary Variable

Data Summaries

Continuous summary statistics will be presented for the mean SKAMP total score for Visits 6 and 7 for the FAS. Similar summaries will be presented for the Completers population.

Primary Efficacy Analysis

A likelihood-based Mixed-effect Model Repeated Measures (MMRM) will be used to assess the primary objective.

In the model, the SKAMP total score for each timepoint will be analyzed with the fixed effects of sequence (two levels), period (two levels), treatment (two levels) and time (10 levels, one for each of 30 minutes prior and 1, 2, 3, 4.5, 6, 7, 9, 10, and 12 hours post dosing) while the repeated measures effect of timepoint will be defined for subject within sequence and ‘Variance Components (VC)’ covariance structure. An example of the SAS procedure to be used is presented below.

```
proc glimmix data=<dataset>;
  class <treatment sequence period timepoint subject>;
  model <SKAMP> = <treatment>
    <sequence>
    <period>
    <timepoint>
```

```
<treatment * timepoint>
/solution ddfm=kr;

random <timepoint> / type=vc subject=<subject * period> residual;
lsmeans <treatment> / pdiff cl alpha=0.05;

estimate 'd-ATS - Placebo' <treatment> -1 1 / cl;
run;
```

Note: *<italics>* identifies where actual variable name substitutions are required.

<sequence> will be required to be defined as <treatment * period> to ensure estimates are obtainable. The two treatment levels will be: d-ATS (5, 10, 15, 20 mg doses combined) and placebo. The treatment * time interaction is included in the model to allow the form of the relationship to be modeled. The purpose of including the interaction term is not to test it for significance and so p-value will not be presented. Raw means, least-squares (LS) means, differences in LS means, and 95% confidence interval (CI) for the difference between treatment arms, and p-values will be calculated for SKAMP total score over the treatment day for the FAS (primary), and Completers populations.

Scaled residual and random effects plots will be considered to check the assumptions behind the mixed model.

Assessment of Carryover

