The sequence effect (treatment x period interaction) will be tested at the significance level of 0.10. If significant differences are detected between sequences, data will be reviewed and strength of evidence indicating a crossover effect will be considered. In this case data from Visit 6 only will be presented to aid in assessment of the treatment effect. When only one period of data is used then the efficiencies gained from conducting a crossover trial design may be lost and there is concern associated with treating data as a parallel study due to the sample size being based up on the assumed efficiencies and may no longer be large enough to provide sufficient power. In this case, permutation test will be used to validate the results. Sampling without replacement (i.e. duplicate samples are not allowed) will be performed for 5000 permutations. The average mean treatment difference will be presented along with the associated 95% confidence interval and p-value for the permutation test. This will be compared against a significance level of 0.05.

Effect Modification Analyses

The primary efficacy analysis on the FAS population will also be conducted for the following subgroups:

- Investigator site
- Optimized dose
- Gender
- ADHD type (inattentive, hyperactive/impulsive, combined, not otherwise specified)
- Baseline ADHD severity (defined as the pre-dose ADHD-RS-IV rating scale for Baseline, Visit 0)

- Age group

To ensure summaries from the subgroups are informative, these will only be performed where subgroups include 5 or more subjects in each. Where subgroups have less than 5 subjects the small group will be combined with the next group, if there is a consecutive order to the groupings or with the next smallest group if there is no order. Baseline ADHD-RS-IV total score will be categorized into the following groups: 0-18; 19-36; and 37-54. Age will be categorized into groups for 6-12 years and 13-17 years.

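### The primary model's diagonal covariance treats up to 20 ratings per child as independent, so the actual level of the 5% test can be well above or below 5%

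*SAP*

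**What the plan says.** SAP 7.1.1 analyses the SKAMP total at ten time points on each of two classroom days. The fixed effects are sequence, period, treatment, time and, in the code, treatment by time. The SAP text says "the repeated measures effect of timepoint will be defined for subject within sequence"; Protocol 8.2.1 says "the repeated measures effect of timepoint will be defined for subject and". Both then name Variance Components as the structure. The only RANDOM statement in the example code is "random <timepoint> / type=vc subject=<subject * period> residual". The procedure call has no empirical option, no subject term appears, and degrees of freedom are Kenward-Roger.

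Three other statements bear on this:

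- **Model checking (SAP 7.1.1):** "Scaled residual and random effects plots will be considered to check the assumptions behind the mixed model". No action is attached to the result.
- **Carryover (SAP 7.1.1):** "The sequence effect (treatment x period interaction) will be tested at the significance level of 0.10". If the test is significant, Visit 6 data are shown alone with a permutation test. The SAP expresses "concern associated with treating data as a parallel study due to the sample size being based up on the assumed efficiencies", so it takes the sample size to depend on within-child comparison.
- **Analysis set (SAP 6.1):** "The FAS population will be used as the primary population for analysis of efficacy endpoints". Children with only one classroom day therefore contribute.

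SAP 7.1.2 (multiple imputation and LOCF) and SAP 7.1.3.2 (PERMP) reuse the same model.

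**The concern.** A residual-side Variance Components matrix has zeros off the diagonal, so the model has no correlation between two ratings of the same child, on the same day or across days. Because the matrix is diagonal, the block named in the SUBJECT option changes nothing, whether it is subject, subject within sequence or subject by period. Kenward-Roger works within the stated covariance and cannot restore a correlation that was left out.

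Two errors follow, in opposite directions. Ratings on one day share that day's deviation, so counting them as independent understates the standard error of a day-average difference. The two days also share the child's own level. A paired comparison removes that variance; this model leaves it in the residual, which overstates the standard error. The net direction depends on variance components that the documents do not give.

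The primary p-value and confidence interval are at stake, and so is the gate to the onset and duration tests, which open only if the primary test is significant. The documents justify MMRM by its control of type I error and minimal bias with missing data. A diagonal model does not secure the first, and it uses none of a child's observed ratings to inform the missing ones. The plan also calls for random-effects plots from a model that has no random effects.

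**Working it through.** **Inputs from the documents.** Two-sided 5% level; 74 completers, 37 per sequence under 1:1 allocation; 90 randomized; 10 sessions × 2 days = 20 ratings per child. The SD and target difference are redacted, so the 74 cannot be reproduced. Read as a paired calculation, it implies a standardised difference of (1.96 + 0.84)/√74 = 0.326.

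**Assumptions.** Total variance 1 = s (subject) + sp (subject by day) + e (session). Let v be the variance of the mean of ten session residuals; v = e/10 if those residuals are independent.

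**Primary contrast.** With complete data and equal session variances, the ratio of true to model variance is r = 10(sp + v), and the level is 2[1 − Φ(1.96/√r)]. This equals 5% only when sp + v = 0.10. In terms of same-day correlation r1 = s + sp and cross-day correlation r2 = s, the same ratio is 1 + 9·r1 − 10·r2.

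Simulation used 10,000 null trials per row, 74 children, the SAP fixed effects with one residual variance, and 1480 − 22 = 1458 df.

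| s / sp / e | r | Level by formula | Simulated |
|---|---|---|---|
| 0.60 / 0 / 0.40 | 0.40 | 0.2% | 0.3% |
| 0.50 / 0 / 0.50 | 0.50 | 0.6% | 0.6% |
| 0.50 / 0.05 / 0.45 | 0.95 | 4.4% | 4.7% |
| 0.50 / 0.10 / 0.40 | 1.40 | 9.8% | 10.1% |
| 0.50 / 0.20 / 0.30 | 2.30 | 19.6% | 20.6% |
| 0.30 / 0.30 / 0.40 | 3.40 | 28.8% | 29.8% |

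At the boundary sp + v = 0.10 the simulated level was 5.2%.

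**Serial correlation within the day.** With shares 0.50/0/0.50 and correlation decaying with elapsed time on the actual schedule, the level is 6.0% at 0.5 per hour and 13.4% at 0.7 per hour.

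**Dropout.** Assume 90 − 74 = 16 children miss the second day at random, 8 per sequence. The rows 0.60/0/0.40, 0.50/0.10/0.40 and 0.30/0.30/0.40 become 4.6%, 16.2% and 31.3%.

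**Power when the test is conservative.** An effect with 80% power under a paired analysis has power Φ(2.80 − 1.96/√r) here: 38% at r = 0.40 and 51% at r = 0.50.

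**Single time points (onset, duration).** r = k(1 − s), where k is that session's variance over the average. With equal variances, the levels were 0.2% to 4% over the shares tried. With four sessions at k = 1.33 and shares 0.20/0.10/0.70, those sessions run at 5.8% to 6.4% and the others at about 1.5%.

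**Sequence test at 10%, if taken from this model.** r = 20(s + sp/2 + v/2).

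| s / sp / e | r | Simulated level |
|---|---|---|
| 0.10 / 0 / 0.90 | 2.9 | 34% |
| 0.20 / 0 / 0.80 | 4.8 | 45% |
| 0.60 / 0.20 / 0.20 | 14.2 | 66% |

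**Analyses that respect the child, on the same simulated data.** The crossover test on post-dose day means ran at 4.8% to 5.4% (complete cases). A bias-corrected sandwich clustered by child on the least-squares fit ran at 4.0% to 4.9%, including the missing-day runs. The sequence test against between-child error ran at 9.3% to 10.5% for nominal 10%.

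**The case against.** **The direction is not fixed.** This is right. Where sp + v is below 0.10, the 5% ceiling holds and the cost is power. The claim is that nothing ties the level to 5%, not that it is always inflated.

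**The code is only an example, and the text may intend a subject variance component.** The wording about subject within sequence and the random-effects plots lend some support to this. But both texts attach Variance Components to the repeated effect of time point. The other reading would not rescue the test either. A random subject effect with independent residuals leaves a within-child residual variance of about e + (10/19)sp, so r = (e + 10sp)/(e + 0.526sp). For the three shares used in the dropout check, r is 1.0, 3.1 and 6.1, and the level is about 5%, 27% and 43%.

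**The shares are not anchored.** This stands. The 30% figure needs subject-by-day variance as large as between-child variance, and the power figures need it to be zero. These are illustrations, but the documents give nothing that would narrow them.

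**The dropout case is extreme.** It assumes all 16 non-completers attend Visit 6. If only eight do (82 children with data), the levels are about 2%, 13% and 30%. The first is again below 5%; the other two remain inflated.

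**The time-point inflation is small.** Agreed; it is a minor consequence.

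**The preferred mixed models were not simulated as written.** This also stands. The checks covered day means and a clustered sandwich on the least-squares fit. On complete data, the day-mean test is equivalent to random subject plus random subject-by-period effects.

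**Conclusion.** The concern holds, and this must be fixed. As written, the confirmatory test has no assured 5% level. Over the assumed shares, with 74 complete cases and equal session variances, the level runs from 0.3% to about 30%. It is near 5% only if subject-by-day variance plus the variance of the mean session residual happens to be about a tenth of the total.

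The sequence test is anti-conservative in every setting shown with child-level variance, provided it comes from this model; the SAP implies this but does not say so. A false positive there leads to a data review, a Visit 6-only presentation and a permutation test. It does not replace the primary result.

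No planned step repairs the primary test. The imputation analyses reuse the model, the permutation test runs only after a significant sequence test, and the residual plots trigger nothing.

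**What to change.** In Protocol 8.2.1, SAP 7.1.1 and the code:

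1. Replace Variance Components with a random subject effect plus a within-day covariance for subject by period that allows unequal session variances, for example unstructured with Kenward-Roger df.
2. Prespecify a fallback for non-convergence that does not assume equally spaced sessions, for example random subject plus random subject by period with empirical standard errors clustered by child and a compatible df method.
3. Alternatively, make the primary test a crossover mixed model with a random subject effect on each child's post-dose day mean. This matches the definition in SAP section 5, but it drops the pre-dose session that the coded contrast averages in. The SAP should say so, and should state how a day with missing sessions is averaged.
4. State which model and error term give the sequence test, and test sequence against between-child error.
5. Use one block definition in the protocol text, the SAP text and the code.

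The cost is revised wording and a little more code, with no new data. The SAP already provides the occasion: "a final version of the SAP, known as SAP2, will be issued for sponsor approval prior to database lock". The unstructured matrix may fail to converge, so the fallback must be written down in advance. The chosen model should be simulated under a few variance shares before it is fixed.

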#### 5.3.4.2 Visit 1 (Day 7), Visit 2 (Day 14), Visit 3 (Day 21), Visit 4 (Day 28) and Visit 5 (Day 35) – Clinic Days

Subjects will return to the clinic for evaluations on Day 7  $\pm$ 3 days, Day 14  $\pm$ 3 days and Day 21  $\pm$ 3 days, Day 28  $\pm$ 3 days and Day 35  $\pm$ 2 days. There must be at least 4 days in between clinic visits). The following evaluations will be performed during each clinic visit:

1. Record any AEs or concomitant therapy since previous visit.

Amendment 4: Version 5.0 May-08-2013

Amendment 3: Version 4.0 December-11-2012

Amendment 2: Version 3.0 October-31-2012

Amendment 1: Version 2.0 August-02-2012

Final Protocol May-25-2012

2. Perform drug accountability and collect all used and unused patches.
3. Review the daily dosing and irritation diaries for compliance.
4. Obtain vital signs (sitting BP, HR, RR, oral body temperature).
5. Record weight.
6. Perform a 12-lead electrocardiogram (ECG) on Day 35.
7. Perform urine pregnancy testing on all female subjects of child-bearing potential.
8. Obtain ADHD-RS-IV score (home version).
9. Perform 1 PERMP (for practice on days 7, 14, 21, and 28) at demonstrated level.
10. Half-day classroom with SKAMP and PERMP (Visit 5, Day 35) pre-dose and 1 and 2 hours post-dose (SKAMP and PERMP rating periods will be 20 minutes in duration).
11. Patch application in clinic (Day 35 only) by subject/parent/caregiver/site personnel
12. Adhesion and discomfort will be evaluated by site personnel after d-ATS patch application at 1 hour and 2 hours/ immediately prior to leaving the clinic on Visit 5 (Day 35).
13. For discomfort scores greater than 0, discomfort will also be evaluated at 1 and 2 hours after d-ATS patch application on Visit 5 (Day 35) using the 10-point Wong-Baker Faces or Visual Analog Scale (age dependent). A  $\pm$  15 minute window is permissible.
14. Site personnel will evaluate skin irritation of the previous day's patch near subject dismissal on Visit 5 (approximately 19 hours after removal of the patch).
15. Administration of the C-SSRS (Children's Since Last Visit version) by a trained staff member.
16. Perform CGI-I.
17. Based on the ADHD-RS-IV score, CGI-I score and side effect profile, adjust the subject's dose to the next available dose (except Visit 4, which can only be a dose reduction and Visit 5 (randomization at optimal dose))

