3.1 SAMPLE SIZE CONSIDERATIONS

Assuming a standard deviation (SD) of [REDACTED] and based on an average difference in total SKAMP scores between Placebo and d-ATS of [REDACTED], 74 subjects would need to complete the study to detect a true difference of [REDACTED] in mean total SKAMP scores between placebo and d-ATS at 80% power when testing at a significance level of $\alpha = 0.05$ (2-sided). Assuming a dropout rate of 20%, 90 subjects will be randomized and it is expected that 74 subjects will complete the study. A subject will be considered to have completed the study if the subject received both treatments during the double-blind Treatment Period and have completed both 12-hour classroom sessions during the double-blind Treatment Period.

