3.2 RANDOMIZATION

Randomization will occur prior to the start of the double-blind study period. Subjects will be randomized to one of the two treatment sequences (d-ATS then Placebo or Placebo then d-ATS) in a 1:1 ratio. Each eligible subject will be randomized to group assignment by a centralized Interactive Voice Response System (IVRS) /Interactive Web Response System (IWRS). Randomization will be applied centrally, without any stratification factors, across all sites to ensure even distribution of subjects across each treatment sequence.

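### The Visit 6-only fallback names no covariate, although a pre-randomised-treatment SKAMP from Visit 5 would make this supportive estimate more accurate

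*SAP*

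**What the plan says.** SAP 7.1.1 (Assessment of Carryover) tests the sequence effect at 0.10. If it is significant, the data are reviewed and the evidence weighed. Protocol 8.2.1 has the same rule: "In this case data from Visit 6 only will be presented to aid in assessment of the treatment effect". The SAP grants that the sample was sized on crossover efficiencies and "may no longer be large enough to provide sufficient power. In this case, permutation test will be used to validate the results". The test uses 5000 permutations of the mean treatment difference, with a 95% CI and a p-value judged at 0.05. Neither document names a covariate for it. SAP 4.3 mentions covariates only as an option in exploratory models.

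Protocol 5.3.4.2 schedules a SKAMP baseline shortly before the double-blind phase: "Half-day classroom with SKAMP and PERMP (Visit 5, Day 35) pre-dose and 1 and 2 hours post-dose". The patch worn that day comes from the open-label pack dispensed on Day 28. Double-blind dosing starts on Day 36 (Protocol 5.1), and SAP 7.4.1 puts it one day after Visit 5. The SAP gives the Visit 5 SKAMP scores no role in the primary or fallback analysis. For the double-blind phase, SAP section 5 takes the same-day pre-dose score as baseline. At Visit 6 that score already follows six days of randomised treatment.

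**The concern.** With one period left, differences between children in SKAMP level enter the error of the treatment comparison. The plan sees the loss, but its only response is a permutation test. That protects validity and does not sharpen the estimate.

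The trigger adds a second problem. The sequence test compares the two groups on the sum of both classroom days, and the Visit 6 difference is part of that sum. Without carryover, the trigger therefore picks out trials in which the two groups differ in SKAMP level by chance. The Visit 6 estimate inherits that imbalance. Randomisation has no stratification factors (SAP 3.2), so nothing in the design limits it. A SKAMP score taken before double-blind treatment measures part of this imbalance and allows it to be removed. What is at stake is the accuracy of an estimate and p-value that are read exactly when the crossover result is in doubt.

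**Working it through.** **Inputs from the documents.** SAP 3.1 gives 80% power, two-sided 0.05, and "74 subjects would need to complete the study to detect a true difference of" a redacted value. It adds: "Assuming a dropout rate of 20%, 90 subjects will be randomized and it is expected that 74 subjects will complete the study". Allocation is 1:1 (SAP 3.2), so Visit 6 alone compares at most 45 v 45, or 37 v 37 among completers.

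**Inputs assumed.** Two correlations are needed and neither is given: rho (Visit 6 with Visit 7 SKAMP) and r (Visit 5 SKAMP with each of these). Both are set to 0.5 unless stated. Units are between-child SDs of a classroom-day SKAMP score.

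**The plan's own figure.** The 74 cannot be reproduced because the SD and the difference are redacted. Under a paired formula it implies delta/SDdiff = (1.960 + 0.842)/sqrt(74) = 0.326 (0.330 with the t distribution). Separately, 74 of 90 is a 17.8% loss rather than 20%, which does not affect this point.

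**Step 1: power if Visit 6 were always analysed alone.** The between-child effect is 0.326 × sqrt(2(1 − 0.5)) = 0.326.
- Unadjusted: 0.326 × sqrt(45/2) = 1.545, so power is Φ(1.545 − 1.960) = 34%.
- Adjusted: the SD is multiplied by sqrt(1 − r²) = 0.866. Then 1.545/0.866 = 1.784, and power is Φ(1.784 − 1.960) = 43%.
- With 37 per group the figures are 28.8% and 36.6%. A simulated permutation test gave 29% and 35%, so permutation by itself recovers nothing.

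**Step 2: error of the estimate once the trigger has fired, no carryover.** For a standard normal S, E(S² | |S| > 1.645) = 1 + 2 × 1.645 × 0.1031/0.10 = 4.39. An estimate with variance V and squared correlation c² with the sequence contrast then has mean squared error V × (1 + 3.39c²).
- Unadjusted: V = 2/45 = 0.0444 and c² = (1 + rho)/2 = 0.75. The MSE is 0.0444 × 3.54 = 0.158, root 0.40.
- Adjusted: V = 0.0444 × 0.75 = 0.0333. The covariance of (Visit 6 − 0.5 × Visit 5) with (Visit 6 + Visit 7) is 1.5 − 0.5 = 1.0, so c² = 1.0²/(0.75 × 3) = 0.444. The MSE is 0.0333 × 2.51 = 0.0836, root 0.29.

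Simulation gives 0.39 and 0.29. The error fell in every setting tried.

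**Step 3: false positives among triggered trials, no treatment effect and no carryover.** Simulation gives about 37% unadjusted and 22% adjusted. The trigger fires in about 10% of such trials, so these are 0.10 × 37% = 3.7% and 0.10 × 22% = 2.2% of all trials.

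**Step 4: power among triggered trials, 45 per group, no carryover (simulated).**

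| rho | r | Unadjusted | Adjusted |
|---|---|---|---|
| 0.5 | 0.3 | 49% | 48% |
| 0.5 | 0.5 | 50% | 47–49% |
| 0.5 | 0.7 | 50% | 54% |
| 0.7 | 0.5 | 51% | 46% |
| 0.7 | 0.7 | 51% | 45% |

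The 9-point gain of step 1 does not carry over. Part of the unadjusted power here comes from the same chance imbalance that produces the 37% in step 3. With strong true carryover the trigger nearly always fires, the selection fades, and the step 1 figures come closer to applying.

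**The case against.** The strongest objection is that little depends on this analysis. The data are presented to aid assessment and the permutation test is there to validate. Nothing says that either replaces the MMRM, and without carryover the branch is reached only about one time in ten. A reader might infer that the primary conclusion would rest on an underpowered test. The documents do not support that, and they already disclose the power concern. This stands, and it limits the weight of the point.

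The covariate may also be weak. Visit 5 is a half-day practice session on open-label drug with ratings to 2 hours, while the Visit 6 mean covers 1 to 12 hours. Children are randomised only after meeting a response rule, which may narrow the range of scores. Half are on placebo at Visit 6, whereas the calculation uses one r for both groups. At r = 0.3 even the step 1 gain is under 5 points (33.9% to 36.7%). This stands as a limit on size. A weak covariate costs one degree of freedom and does not make the comparison invalid.

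An unadjusted analysis is read from silence. That is fair, but the text describes a mean difference and names no covariate. Finally, if the 74 came from a two-group formula (37 per group, delta/SD 0.651), Visit 6 alone would keep about 80% power. The SAP's remark about crossover efficiencies argues against that reading.

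**Conclusion.** The point holds as a refinement of a supportive analysis. A SKAMP score that precedes double-blind treatment is already collected, and the Visit 6-only comparison does not use it. With 45 per group, no carryover and both correlations at 0.5, using it cuts the error of the triggered estimate from about 0.39 to 0.29 SD, and false positives among triggered trials from about 37% to 22%.

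Two stronger readings should be resisted. One is that adjustment raises the power of the fallback from 34% to 43%. Those figures ignore the trigger and rest on a paired reading of the 74. Once the trigger has fired, power may be unchanged, higher or lower, depending on carryover and correlations that the plan does not give. The other is that adjustment makes the fallback sound. A rate of 22% is still far above 5%, because the inflation comes from the test-then-drop-a-period rule, which a covariate reduces but does not cure.

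The size rests on assumed correlations and the direction of the accuracy gain does not, provided Visit 5 SKAMP is correlated with Visit 6 SKAMP. This is a change to consider rather than one the plan must have.

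**What to change.** In SAP 7.1.1 (Assessment of Carryover), state the following:
- The Visit 6-only estimate, 95% CI and p-value come from an ANCOVA of the Visit 6 mean post-dose SKAMP total on treatment and the mean of all three Visit 5 SKAMP totals (pre-dose, 1 h, 2 h). Name all three, because the mean defined in SAP section 5 leaves out the pre-dose score.
- A child with no Visit 5 SKAMP receives the overall mean of the covariate.
- The permutation test uses the ANCOVA treatment coefficient or its t statistic, and refits the model for each permuted assignment. Permuting labels against residuals from a regression on Visit 5 alone is a different statistic when the covariate is imbalanced.
- The same-day Visit 6 pre-dose score is not used as the covariate.
- The unadjusted result is kept as supportive, and the whole Visit 6-only analysis is labelled as supportive of the MMRM.

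The cost is a short SAP paragraph, one covariate in the program and one degree of freedom, with no new data. The gain is small if the practice session correlates weakly with Visit 6. SAP section 1 provides for a final version before database lock, and the choice should be fixed there, because a covariate chosen after a significant sequence test would look data-driven.

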4.3 PREDETERMINED COVARIATES AND PROGNOSTIC FACTORS

Demographic and baseline characteristics known to be related to treatment response may be considered for inclusion as covariates in exploratory statistical analysis models.

The effect of the following factors on the primary efficacy analysis (FAS population) will be considered:

- Investigator site
- Optimized dose
- Gender
- ADHD type (inattentive, hyperactive/impulsive, combined, not otherwise specified)
- Baseline ADHD severity (defined as the pre-dose ADHD-RS-IV rating scale at baseline, Visit 0)
- Age group

To ensure summaries from the subgroups are informative, these will only be performed where subgroups include 5 or more subjects in each. Where subgroups have less than 5 subjects the small group will be combined with the next group, if there is a consecutive order to the groupings or with the next smallest group if there is no order.

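### The SAP's effect modification section reruns the primary model within each subgroup level and plans no estimate or test of whether the treatment effect differs between levels.

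*SAP*

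**What the plan says.** SAP 7.1.1, under Effect Modification Analyses, states: "The primary efficacy analysis on the FAS population will also be conducted for the following subgroups", and lists investigator site, optimized dose, gender, ADHD type, baseline ADHD severity and age group. The same section says the primary analysis yields LS-mean differences, 95% confidence intervals and p-values, so a rerun yields these for each level.

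On size, "these will only be performed where subgroups include 5 or more subjects in each". Below that number, "Where subgroups have less than 5 subjects the small group will be combined with the next group" if the levels are ordered, and otherwise with the next smallest.

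SAP 4.3 lists the same factors: "The effect of the following factors on the primary efficacy analysis (FAS population) will be considered". It adds that demographic and baseline characteristics "may be considered for inclusion as covariates in exploratory statistical analysis models".

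Two interactions are named in the SAP, and neither involves a subgroup factor. For treatment by time, "The purpose of including the interaction term is not to test it for significance and so p-value will not be presented". The other is for carryover: "The sequence effect (treatment x period interaction) will be tested at the significance level of 0.10".

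Protocol 8.2.1 plans the same subgroup reruns, with no minimum size and no interaction test.

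**The concern.** Effect modification is a statement about the difference between two treatment effects. Fitting the primary model separately in each level asks a different question, namely whether each level's own effect differs from zero. One level can reach significance and another miss it when the effects are identical, merely because one group is smaller or less lucky.

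Up to 18 within-level p-values are foreseen before any pooling: 3 sites + 4 doses + 2 genders + 4 ADHD types + 3 severity bands + 2 age groups. Without an estimate of the difference beside them, the readiest comparison is of which levels reached significance. That could produce a statement that d-ATS works in one group and not in another which the data do not support. What is at stake is the reading of the subgroup tables, not the primary result.

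**Working it through.** **Inputs.** SAP 3.1 gives 74 completers, 80% power and two-sided alpha 0.05. SAP 7.1.1 gives the minimum of five subjects per level. The SD and difference are redacted, so the 74 cannot be rebuilt from its own inputs. No subgroup sizes are given, so the splits 37/37, 55/19 and 69/5 of the 74 completers are assumptions chosen to span even to very uneven.

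**Step 1: effect implied by the sample size.** Let d be the mean within-subject difference divided by its SD, with one mean score per subject per classroom day. By the normal approximation, d = (1.960 + 0.842)/√74 = 2.802/8.602 = 0.326. By the noncentral t with n − 2 degrees of freedom, d = 0.330. I use 0.330, and repeat at 0.5, 0.65 and 0.8 because the true effect may be larger.

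**Step 2: power within a level.** Power(n) = P(|T| > t(0.975, n − 2)), with T noncentral t on n − 2 degrees of freedom and noncentrality d√n. At d = 0.330:

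- n = 69: 0.771
- n = 55: 0.671
- n = 37: 0.497
- n = 19: 0.274
- n = 5: 0.083

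At n = 5 the 95% interval has half-width 3.182/√5 = 1.42 SD, about 4.3 times the effect of 0.330.

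**Step 3: disagreement under a constant effect.** Levels contain different subjects, so their tests are treated as independent. With powers p and q, P(exactly one significant) = p(1 − q) + q(1 − p).

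- 37/37: 2 × 0.497 × 0.503 = 0.50
- 55/19: 0.671 × 0.726 + 0.274 × 0.329 = 0.58
- 69/5: 0.771 × 0.917 + 0.083 × 0.229 = 0.73

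The same calculation over the range of effects:

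| d | 37/37 | 55/19 | 69/5 |
|---|---|---|---|
| 0.33 | 50% | 58% | 73% |
| 0.5 | 27% | 47% | 86% |
| 0.65 | 6% | 24% | 82% |
| 0.8 | 1% | 9% | 76% |

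With an even split the problem fades as the effect grows. With a very small level it persists, because the large level is almost always significant and the small one usually is not (power at n = 5 is 18% at d = 0.65).

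**Step 4: what an interaction test would offer.** The SE of the difference between two levels is √(1/n1 + 1/n2) in SD units, with n1 + n2 − 4 = 70 degrees of freedom. For an interaction equal to the overall effect, the noncentrality is 0.330 divided by that SE:

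- 37/37: 0.330/0.232 = 1.42, power 29%
- 55/19: 0.330/0.266 = 1.24, power 23%
- 69/5: 0.330/0.463 = 0.71, power 11%

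For 80% power the interaction would have to be about 2.0, 2.3 and 4.0 times the overall effect.

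**The case against.** The strongest reply is that these are descriptive consistency checks. They lie outside the formal testing sequence in SAP 7, SAP 7.1.1 itself speaks of subgroup summaries, and Protocol 8.2.1 lists the subgroups without the term effect modification. Nothing says that p-values will be compared across levels or that a subgroup claim will be made. This stands, and it limits the consequence. It does not supply the missing estimate, and the SAP heading promises one.

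A reader might infer that the planned output cannot show effect modification at all. That goes too far: the levels are separate subjects, and their differences and intervals are reported, so anyone could form the contrast and its standard error by hand. The plan simply does not do so.

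A reader might also take five as the planned size. It is the threshold below which levels are pooled, and it tightens a protocol that had none. The documents give no expected subgroup sizes.

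Nor does the 50% figure hold generally. It belongs to an even split at the back-solved effect, and at 0.65 it falls to 6%. The calculation also uses one mean per day, whereas the planned model uses ten ratings per day with a variance components structure, so the p-values that model prints may behave differently.

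Finally, the interaction test is weak and could be misread in the other direction. This is correct, and the remedy has to say so.

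**Conclusion.** The point holds in a limited form. SAP 7.1.1 plans per-level differences, intervals and p-values, but no estimate or test of whether effects differ between levels, and SAP 4.3 and Protocol 8.2.1 do not fill the gap. Under a constant effect, disagreement on significance ranges from about 1% (even split, d = 0.8) to 86% (69/5 split, d = 0.5). How often it would occur here depends on the redacted effect and on subgroup sizes that the documents do not give. The figures assume 74 completers, equal variance across levels and one mean score per subject per day.

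This is a mismatch between question and method in an exploratory section. A reader might infer that it weakens the efficacy finding. It does not: the primary, onset and duration analyses do not use these results.

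**What to change.** For each factor, fit one model on the whole FAS, adding the factor and the treatment-by-factor interaction to the primary model. Report:

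- the interaction as differences in treatment effect between levels, with 95% confidence intervals, and its p-value (a joint test where there are more than two levels);
- the treatment difference with 95% confidence interval in each level, from that same model.

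Label all of it exploratory, and state that within-level p-values will not be used to judge effect modification. Keep the pooling rule.

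The cost is two added terms per model and a little more programming and reporting, with no new data. SAP 1 already provides for a final SAP version before database lock, which can carry the change. The single model also assumes that period and time effects and residual variance are common to all levels, which the separate fits do not.

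The main drawback is the low power shown above. The text should therefore put the estimate and interval ahead of the p-value, and say that a non-significant interaction does not establish a uniform effect. If the sponsor prefers not to add the model, the minimum is to retitle the section as descriptive subgroup summaries and include the same caution about within-level significance.
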